**1a) Is this study considered human research?**

- Yes
- No
- I don't know

**1b) Please select:**

- This is an application for a NEW human subject research protocol
- This is a revision of an existing protocol

**Section 2 - Research Subjects**

**2a) What is the total planned number of VA-consented subjects?**

Include the total number of subjects who will prospectively agree to participate in the study (e.g., documented consent, oral consent, or other).

88

## 2b) What is the total number of VA subjects who WILL NOT be consented?

Include the total number of subjects that will be included without consent (e.g., chart review). *Note: Data about people are still considered "human subjects" by the IRB, so even if you do not intend to contact the patients whose charts you will review, you still should enter the number of charts as your "planned subjects."*

0

## Section 2.1 Consented Subject Groups

### 2.1) For each of the subject categories listed below, indicate whether or not these subject groups will participate in the study:

2.1a) Children under the age of 18

*Note: If neonates or children will be involved in this study, certification by the Medical Center Director will be required. Only minimal risk research may be performed with children. Only non-invasive monitoring and/or prospective observational and retrospective record review studies that are minimal risk can be conducted in VA involving neonates.*

Yes  No

2.1b) Pregnant women

Yes  No

2.1c) Individuals with cognitive/decisional impairment

Yes  No

2.1d) Non-English-speaking individuals

Yes  No

2.1e) Prisoners of War (explicitly targeting this group)

Yes  No

2.1f) Non-Veterans (Note: Justification for inclusion of non-Veterans will be required)

Yes  No

2.1g) Incarcerated individuals (Note: VA CRADO approval will be required)

Yes  No

2.1h) VA employees - including VA paid, IPA, or WOC (Note: Union review and authorization may be required)

Yes  No

2.1i) Students of the institution (e.g., resident trainees) or of the investigator

Yes  No

2.1j) Patients with cancer (or high cancer risk) [explicitly targeting this group]

Yes  No

## Section 3 - Study Features (these items default to "No" for convenience)

3) This section consists of several Yes/No questions addressing protocol characteristics. [Click on Save and](#)

Continue.

### Section 3.1 Protocol Basics

#### Select all that apply

3.1a) The research **intends to change** the participant.

Yes  No

3.1b) **Interactions** with living participants to collect data or specimens with no intent to change them.

Yes  No

3.1c) This is a study that **never** has any **subject contact and does not collect subject identifiers**

Yes  No

3.1d) This is a **chart review** study involving retrospective or prospective medical records.

Yes  No

3.1e) This is a **multi-site** study occurring in-part or in-full at other locations.

Yes  No

3.1f) There is an **international** component to this research. *International research includes sending or receiving human derived data or specimens (identifiable, limited data set, coded, or deidentified) to or from an international source. International research does not include studies in which VA is only one of multiple participating sites where the overall study-wide PI is not a VA investigator.*

Yes  No

3.1g) This study includes **off-station activity** (not including VA-leased space or CBOC clinics) conducted under VASDHS IRB approval. *Note: this does not include research conducted by a collaborator at their home institution under their institutional approval.*

Yes  No

3.1h) VA subjects will **participate** in part or in full **at other locations** (not including VA-leased space or clinics) under VASDHS IRB approval. *Note: if this study involves remote participation of subjects, please indicate "no" and describe their remote participation in section 9 of the application. This question is intended to understand whether participants must physically go to a non-VA location to participate in this VA research study.*

Yes  No

### Section 3.2 Specimen Use and Data Repository

#### Indicate whether or not each of the following applies to this protocol

3.2a) Involves specimens that are left over from pathological or diagnostic testing (**non-research specimens**)

Yes  No

3.2b) Involves **specimens collected for research purposes only**

Yes  No

3.2c) This study includes **specimen banking** (specimens are retained for use outside of the purposes of this protocol)

Yes  No

3.2d) The study involves **DNA** genotyping or other **genetic analysis**

Yes  No

3.2e) Biological **specimens/material** will be sent outside of the VA.

Yes  No

3.2f) A **data repository** is maintained (data are retained after completion of the protocol for other uses, IMPORTANT: see ? before checking "yes")

Yes  No

3.2g) **Data will be shared outside** of the VA (identifiable, coded, limited data set, or deidentified)

Yes  No

### Section 3.3 Treatment and Clinical Trials

#### Indicate whether or not each of the following applies to this protocol

3.3a) Includes a **treatment** component (a research treatment)

Yes  No

3.3b) Study is a **clinical trial**. *Note: A clinical trial is a research study in which one or more human subjects are prospectively assigned to one or more interventions (which may include placebo or other control) to evaluate the effects of the interventions on biomedical or behavioral health-related outcomes.*

Yes  No

3.3c) Has a data safety monitoring board (**DSMB**) or data safety monitoring committee.

Yes  No

3.3d) Has a **data safety monitoring plan** (but not a DSMB) (this is not the data security plan, it is a safety plan).

Yes  No

### Section 3.4 Drugs and Devices

#### Indicate whether or not each of the following applies to this protocol

3.4a) **Drugs** that require **FDA** action such as an Investigational New Drug (IND) approval or exemption or 510 (k) approval.

Yes  No

3.4b) Other drugs, supplement, etc. that **do not require FDA** action for inclusion in the study.

Yes  No

3.4c) Medical **devices requiring FDA IDE** approval or waiver

Yes  No

3.4d) **Other medical devices**

Yes  No

### Section 3.5 Risk and Hazards

#### Indicate whether or not each of the following applies to this protocol

3.5a) Study places subjects at **greater than minimal risk** (do not include risks that are due to standard care)

Yes  No

3.5b) Human subjects are exposed to **radioisotopes** (do not include standard care).

Yes  No

3.5c) Subjects have other **radiation exposure** (e.g., x-rays) (do not include standard clinical use).

Yes  No

3.5d) Target population has psychiatric diagnosis, behavioral complaint, or chronic pain.

Yes  No

## Section 3.6 Clinical Facilities and Standard Care

### Indicate whether or not each of the following applies to this protocol

3.6a) Study **uses VA clinical services** (e.g., adds required tests run in the VA lab for study purposes; research procedures concurrent with clinical care)

Yes  No

3.6b) Includes procedures or drugs that will be considered **part of standard care**.

Yes  No

3.6c) Involves **lab tests done for research purposes**.

Yes  No

## Section 3.7 Subject Expenses and Compensation

### Indicate whether or not each of the following applies to this protocol

3.7a) There may be expense or added **costs to the subject** or the subject's insurance.

Yes  No

3.7b) This is a **qualifying cancer treatment trial** and subjects may be billed for study drugs or procedures.

Yes  No

3.7c) This is a cancer treatment trial but **subjects will not be billed** for study drugs or procedures.

Yes  No

3.7d) Subjects will be **compensated** (either in cash or other means such as a gift certificate).

Yes  No

## Section 3.8 Subject Activities

### Indicate whether or not each of the following applies to this protocol

3.8a) Involves **surveys or questionnaires** completed by subjects

Yes  No

3.8b) Includes the use of **recruitment materials** such as flyers, advertisements, or letters

Yes  No

3.8c) Involves facial **photographs** or audio or video **recordings** of patients

Yes  No

## Section 3.9 Sponsors and Collaboration

Indicate whether or not each of the following applies to this protocol

3.9a) This research is a funded research project (**commercial (industry) sponsor, NIH, VA, other**).

Yes  No

3.9b) Other **commercial (industry) non-financial support** is provided (e.g., drugs or supplies).

Yes  No

3.9d) The protocol has **Department of Defense** involvement (e.g., subjects or funding).

Yes  No

3.9c) The PI or other study staff member has a financial interest or other **real or potential conflict** related to this study.

Yes  No

3.9e) This study involves **collaborative** research activities (research conducted at other institutions under the authorities or approvals of the other institution/s). *Note: this may include other VA and/or non-VA institutions, but does not include off-site VA research.*

Yes  No

## Section 4 - Estimated Duration

4) What is the estimated duration of the entire study? (From IRB approval to IRB closure)

5 years

## Section 5 - Lay Language Summary

5) Provide a summary or synopsis of the proposed study using non-technical language (not more than 1 paragraph)

The overall aim of this longitudinal RCT is to determine the efficacy of MBSR to improve HRQoL, cognition, and mood, as well as to determine the longevity of the treatment response in individuals with PD. We hypothesize that HRQoL, cognition (particularly executive function), and mood (particularly anxiety) symptoms (will improve in PD participants following eight weeks of MBSR compared to PD participants randomized to an eight-week active Psychoeducational control condition. We further hypothesize that benefits of MBSR treatment will be evident at the 6- and 12-month assessments, such that those completing the MBSR group will demonstrate better HRQoL, cognition, and mood relative to those PD patients who completed the Psychoeducational Supportive Care (PSC) group. Potential mediators/moderators of the treatment response will be examined in exploratory hypotheses. Eighty-eight non-demented individuals with PD will be recruited and enrolled in the proposed study. Over-recruitment by 10% will be instituted to account for subject attrition or unusable data, and to ensure an adequately-powered sample size of 80 (40 per group). Participants will be randomized into either eight weeks of MBSR (n = 44) or eight weeks of PSC (n = 44). All participants will be administered a battery of neuropsychological tests to measure HRQoL, cognition (e.g., executive function, attention, memory), and mood (i.e., anxiety, depression, and apathy), as well as motor symptoms, disease severity, and mindfulness engagement/practice. Tests will be administered at baseline, 8 weeks (post-treatment), and 6- and 12-months (follow-up assessments) by an examiner blinded to group assignment. Data will be primarily analyzed using linear and multivariable random effects modeling. Findings from this study will provide critical information regarding the efficacy of MBSR for HRQoL, cognition, and mood in PD. Furthermore, results will

provide essential data regarding the long-term benefits of MBSR in PD, and elucidate potential mediators/moderators of treatment response.

## Section 6 - Specific Aims

### 6) Provide a statement of specific aims and hypotheses that serve as the basis for this protocol. Emphasize those aspects that justify the use of human subjects.

Aim 1. To investigate the efficacy of MBSR to improve health-related quality of life in PD. Hypotheses: PD patients who complete MBSR will demonstrate (Primary Hypothesis 1a) greater improvement in HRQoL from baseline to post-treatment compared to PD participants randomized to a duration- and frequency-matched psychoeducational/supportive care control group; and (Hypotheses 1b) better HRQoL at the 6- and 12-month follow-up evaluations.

Aim 2. To examine the efficacy of MBSR to improve cognition in PD.

Hypotheses: PD patients who complete MBSR will demonstrate (Hypothesis 2a) greater improvement in cognition from baseline to post-treatment compared to PD participants randomized to a duration- and frequency-matched psychoeducational/supportive care control group, and (Hypotheses 2b) better cognition at the 6- and 12-month follow-up evaluations.

Aim 3. To determine the efficacy of MBSR in reducing mood symptoms in PD.

Hypotheses: PD patients who complete MBSR will demonstrate (Hypothesis 3a) greater improvement in mood from baseline to post-treatment compared to PD participants randomized to a duration- and frequency-matched psychoeducational/supportive care control group, and (Hypotheses 3b) better mood at the 6- and 12-month follow-up evaluations.

Exploratory Aim: To examine the mediators and moderators of treatment response on HRQoL following MBSR in PD. As cognitive and mood symptoms are associated with poor HRQoL in PD, we hypothesize that HRQoL change will be mediated and/or moderated by changes in cognition and mood from pre- to post-intervention. We will test the possible moderation/mediation effects of non-motor and motor symptoms on HRQoL following MBSR at 8 weeks (post-treatment), and 6- and 12 months.

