## Section 7 - Background and Significance

### 7) Provide a succinct discussion of relevant background information to justify performing the proposed study.

Over 80,000 Veterans with Parkinson's disease (PD) currently obtain their medical care within the VA Healthcare System and the number of Veterans with PD is expected to increase in the near future. Health-Related Quality of Life (HRQoL) is severely compromised in those with PD and worsens as the disease progresses. Non-motor symptoms, particularly cognition and mood, which also progressively decline over the course of the disease, contribute to poor and worsening of HRQoL in PD. Interventions that target these symptoms and improve HRQoL are critically needed. Mindfulness-based Stress Reduction (MBSR) is a non-pharmacological intervention that has been shown to improve HRQoL as well as improve mood and attenuate cognitive decline in older adults with and without neurological disorders. Although preliminary evidence supports MBSR as a promising intervention for PD, there has yet to be a comprehensive randomized controlled trial (RCT) of MBSR in this population. Results from our pilot trial ( $n = 20$ ) demonstrated that PD participants who completed an 8-week MBSR program ( $n = 8$ ) evidenced an improvement in overall HRQoL ( $d' = 1.14$ ), cognition (executive function;  $d' = 1.6$ ), and mood (anxiety;  $d' = 1.1$ ) compared to PD participants in an active control condition (Psychoeducation/Supportive Care;  $n = 12$ ); the latter of whom experienced a worsening of symptoms. These findings provide convincing preliminary evidence of MBSR efficacy for PD. In the proposed RCT, we will determine the efficacy of MBSR to improve HRQoL, cognition, and mood in a larger PD sample as well as determine the longevity of the treatment response.

Findings from this study will provide critical information about the efficacy of MBSR for HRQoL, cognition, and mood in PD. Furthermore, results will provide essential data regarding the long-term benefits of MBSR for non-motor symptoms in PD and elucidate potential mediators/moderators of the treatment response. Ultimately, this study will test a potential efficacious treatment for PD that could be widely implemented and disseminated throughout the VA Healthcare System and beyond.

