Those who meet criteria will be administered the pre-intervention neuropsychological battery within approximately one week prior to beginning the group by an examiner who will be blinded to group assignment. Participants will be group randomized to one of two 8-week conditions (i.e., 6-8 participants assigned in groups via R randomizer to either Mindfulness Based Stress Reduction (MBSR) or Psychoeducational Supportive Care). All activities will be conducted on the VA San Diego campus. MBSR and Psychoeducational Supportive Care groups will each consist of approximately 6-8 individuals with PD and be led by a trained instructor who is not involved in the clinical care or assessment of these participants. Participants will meet in groups for 2.5 hours once per week for eight weeks, with a 2.5 hour session ("retreat") between weeks 6 and 7. Each week and at the start of group, all participants will complete a brief form regarding changes in mood and medications. Any changes in mood will be addressed by clinicians on the protocol to assess for SI (please see MCM 11-24 Suicidality attached to protocol). We will offer assistance during each session to escort those who are at risk for falling (i.e., UPDRS fall item #13 > 0) to the bathroom and to and from their vehicle as appropriate.

All participants will be administered a battery of neuropsychological tests to measure HRQoL, cognition (e.g., executive function, attention, memory), and mood (i.e., anxiety, depression, and apathy), as well as motor symptoms, disease severity, and mindfulness engagement/practice. The UPDRS Part-III/Hoehn and Yahr Score (HYRS), which assess level of motor function and characterizes disease severity, will also be administered by study staff, certified in UPDRS administration, at their baseline assessment. If we are unable to obtain this score, we will obtain a ROI to access their UPDRS exam score(s) and HYRS. Tests will be administered at baseline, 8 weeks (post-treatment), and 6- and 12-months (follow-up assessments). Breaks will be offered and given during the assessment as needed. Study questionnaires are attached to the protocol submission.

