Following the intervention and 6- and 12-months post-intervention, PD participants will be re-tested by a group-blinded research assistant. The UPDRS Part-III/HYRS will also be administered by study staff, certified in UPDRS administration, at the 12-month follow up appointment as well. Total participation time is 2-3 hours per session x 4 total sessions (-pre, -post, -6, and -12 month follow up). To better retain participants throughout the 12-month trial period, we will implement friendly reminder calls at 2-months and 1-month prior to each testing session as well as send a reminder letter with pertinent information (e.g., directions) 2-3 weeks prior to their appointment. In addition, MBSR will be offered to the Psycheducational Supportive group participants upon study completion.

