### Data Analysis

Data will be primarily analyzed using linear and multivariable random effects modeling.

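### The primary hypothesis compares MBSR completers with everyone randomised to control, and no text replaces this with an as-randomised comparison

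*Combined protocol and SAP*

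**What the plan says.** Section 6 (Specific Aims) gives the primary hypothesis as "PD patients who complete MBSR will demonstrate (Primary Hypothesis 1a) greater improvement in HRQoL from baseline to post-treatment compared to PD participants randomized to" a matched psychoeducational/supportive care group. Hypotheses 2a (cognition) and 3a (mood) have the same form: completion defines the MBSR side, randomisation the control side. The b hypotheses (6 and 12 months) share the subject, patients who complete MBSR, and name no separate comparator.

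Section 5 (Lay Language Summary) words the follow-up comparison differently: "those completing the MBSR group will demonstrate better HRQoL, cognition, and mood relative to those PD patients who completed" the control programme. That is completers on both sides.

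The Data Analysis text in Section 9 is one sentence: "Data will be primarily analyzed using linear and multivariable random effects modeling". It does not say which participants enter the model. No supplied text states an intention-to-treat or as-randomised rule, defines completion, or says how someone who stops, or who rejoins a later group as Section 15 allows, is analysed.

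On numbers, Section 5 plans 44 randomised per arm and a final 40 per arm: "Over-recruitment by 10% will be instituted to account for subject attrition or unusable data". On follow-up, Section 9 schedules testing without a completion condition: "All participants will be administered a battery of neuropsychological tests to measure HRQoL, cognition". It adds retention effort: "we will implement friendly reminder calls at 2-months and 1-month prior to each testing session". Section 20 pays for each testing session.

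**The concern.** Randomisation makes the two arms comparable as assigned. A contrast that keeps only those who finished MBSR but keeps everyone assigned to control gives up that protection on one side. If people who stop MBSR would have done worse anyway, removing them makes MBSR look better with no treatment effect at all.

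The documents make outcome-related stopping possible. Section 15 foresees that medical or psychological changes may end participation early. Section 9 has a weekly check in both arms ("all participants will complete a brief form regarding changes in mood and medications"), and under Section 15 a reported mood change leads to an evaluation of whether the person continues. Mood is the Aim 3 outcome.

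There is also a choice left open. Sections 5 and 6 describe two different populations, neither of them all randomised participants in both arms, and the analysis sentence fits either of them or an as-randomised analysis. The analysis set could therefore be settled after the data are seen.

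**Working it through.** **The plan's own figure.** 80 x 1.10 = 88, or 44 per arm, as stated. The allowance is 8/88 = 9.1% for attrition or unusable data over both arms. It is not a non-completion rate for MBSR, so it is not used as one below.

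**Assumed inputs.** The documents give neither of these:
- p: the share of an arm that stops the sessions, taken as equal in both arms.
- g: how many SD worse stoppers do than completers.

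Other settings: 44 per arm, total SD 1, no as-randomised effect, two-sided t-test at 0.05 (no alpha is stated), clustering by group and baseline adjustment ignored, 200,000 simulated trials per case.

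**Formula.** Put the overall mean at 0. MBSR completers then have mean p x g. If a fraction f of control stoppers is still assessed, the share of stoppers among assessed controls is s = f x p / (1 - p + f x p), and their mean is (p - s) x g. The bias of the worded contrast is the difference, s x g.

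**All control stoppers assessed (f = 1, so s = p and bias = p x g):**

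| p | g | Bias (SD) | Two-sided type I error |
|---|---|---|---|
| 5% | 0.5 | 0.025 | 5.1% |
| 10% | 0.5 | 0.05 | 5.7% |
| 20% | 0.5 | 0.10 | 7.1% |
| 30% | 0.5 | 0.15 | 9.6% |
| 20% | 1.0 | 0.20 | 14.5% |
| 20% | 0 | 0 | 5.0% |
| 20% | -0.5 | -0.10 | 7.2% |

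**Fewer control stoppers assessed (p = 20%, g = 0.5):**
- f = 0.5: s = 0.10/0.90 = 0.111, bias = 0.111 x 0.5 = 0.056 SD, type I error about 5.5%.
- f = 0: s = 0, bias 0, about 5.0%. This is the completers-against-completers case with equal stopping.

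**As-randomised contrast, all outcomes observed (g = 0.5, p = 10% or 20%):** bias 0, type I error 5.0%.

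**Price of the as-randomised contrast.** If non-attenders gain nothing, a true effect d is estimated as d x (1 - p). The documents give no design effect, so take d = 0.634, which 40 per arm detects with 80% power. With 44 per arm, all observed:
- p = 0: d = 0.634, power 84%.
- p = 10%: 0.634 x 0.9 = 0.571, power 75%.
- p = 20%: 0.634 x 0.8 = 0.507, power 65%.

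The one-arm completer contrast would have 82% and 79% power at p = 10% and 20%, but is unbiased for the effect in attenders only when stopping is unrelated to outcome.

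**The case against.** The strongest reply is that the word *complete* is shorthand for being in the MBSR arm. Several places fit that. Sections 5 and 9 plan the same loss, 44 to 40, in both arms, which one-sided exclusion would not suggest. Section 9.11 has facilitators record attendance and lists engagement and practice among things to examine in analyses, not as a filter. A random effects model can hold every randomised participant. This stands as a reason for caution, but none of it is a rule on who is analysed.

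Three stronger readings are tempting and are not supported:
- A reader might infer that a completer analysis is planned. No text says that anyone will be excluded.
- A reader might infer that the mood check builds in bias towards MBSR. The exits in Section 15 are from the study, not only from the sessions, and apply to both arms. Someone who leaves before the post-treatment visit has no outcome in either arm, which moves towards the zero-bias case. Section 15 also calls the foreseen changes unrelated to the study, and the weekly form gives no direction of mood change.
- A reader might take the pilot in Section 7 ("PD participants who completed an 8-week MBSR program", n = 8, against 12 controls) as precedent. But 8 + 12 = 20 is the whole stated pilot, and the number randomised is not given. It does not settle the point either way.

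It is also fair that the illustrated effect is small at low non-completion, and that no text suggests a high rate.

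**Conclusion.** The point holds as a defect in the stated contrast. It does not show that a biased analysis is planned. The primary hypothesis, followed as worded, conditions one arm on a post-randomisation event, and nothing in the supplied text replaces it.

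The size is unknown. It reaches 0.10 SD and about 7% type I error only with all of three assumptions: about 20% of the arm stops, stoppers do 0.5 SD worse, and control stoppers are still tested. Relaxing any one of them shrinks the bias, to nothing at the limit. If stoppers do better, it reverses. Follow-up is not the weakness, because testing is scheduled for all participants. The change is worth making because it is cheap and fixes the primary comparison before data are seen.

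**What to change.** - In Section 6, word Hypotheses 1-3 (a and b) as participants randomised to MBSR versus participants randomised to PSC, and align Section 5.
- In Data Analysis, add that the primary random effects model includes every randomised participant in the assigned arm with all observed visits, whatever the attendance and including anyone who rejoins a later group.
- Label any completer comparison as secondary.

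This costs a rewording and one or two sentences. The enrolment of 88 and the visit schedule do not change. The real price is the dilution shown above. Rewording also does not recover outcomes of people who leave the study altogether. For them the result still rests on the model's missing-data assumption.

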## Section 9.8 Questionnaires & Surveys

**9.8) Provide the name and a reference for questionnaires/surveys that are standard or identify them here and attach a copy of the questionnaire/survey. *Questionnaires or surveys that are not clinical standard references must be uploaded. Reference the help link for additional information related to surveys administered to VA personnel and approved platforms for web-based surveys.***

Beck Depression Inventory (BDI-II)

The Parkinson's disease Questionnaire-39 (PDQ-39)

Spielberger State-Trait Anxiety Inventory (STAI/TRAIT)

Geriatric Depression Scale (GDS)

Starkstein Apathy Scale (AS)

Five Facet Mindfulness Questionnaire (FFMQ-15)

Credibility and Expectancy Questionnaire (CEQ)

Client Satisfaction Questionnaire (CSQ-8)

Mindfulness Based Stress Reduction Practice Log

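### The Exploratory Aim names no control contrast and lets post-randomisation changes act as moderators; it should specify two-arm interaction and mediation models

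*Combined protocol and SAP*

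**What the plan says.** Section 6 (Specific Aims) sets the exploratory objective: "To examine the mediators and moderators of treatment response on HRQoL following MBSR in PD". Three features of that paragraph matter.

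- **Contrast.** The test is worded as "We will test the possible moderation/mediation effects of non-motor and motor symptoms on HRQoL following MBSR at 8 weeks (post-treatment), and 6- and 12 months". No comparator is named. Hypotheses 1a, 2a and 3a in the same section each are: "compared to PD participants randomized to a duration- and frequency-matched psychoeducational/supportive care control group".
- **Roles.** The hypothesis is that "we hypothesize that HRQoL change will be mediated and/or moderated by changes in cognition and mood from pre- to post-intervention". The same change scores may therefore be mediators, moderators or both.
- **Rationale.** The candidates are chosen on this ground: "As cognitive and mood symptoms are associated with poor HRQoL in PD". That is a general association in the disease, not one specific to MBSR.

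Section 5 adds only that "Potential mediators/moderators of the treatment response will be examined in exploratory hypotheses", and Section 7 repeats the promise in similar terms. The Data Analysis paragraph of Section 9 is a single sentence naming linear and multivariable random effects models. It has no arm-by-covariate term, mediation path or estimand.

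On measurement, Section 9 (Assessments and Intervention) has HRQoL, cognition and mood assessed in all participants at baseline, 8 weeks, 6 months and 12 months. UPDRS Part III with Hoehn and Yahr is scheduled at baseline and 12 months only.

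**The concern.** A moderator of a randomised treatment effect is a characteristic across which the difference between arms varies. A mediator is a variable that the treatment moves and that in turn moves the outcome. Both definitions need the control arm. Within the MBSR arm alone, a baseline score that predicts HRQoL change may do so equally under psychoeducational supportive care, and is then only prognostic. Likewise, a mood change that tracks HRQoL change may track it equally in controls and owe nothing to MBSR.

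Taken literally, the Exploratory Aim describes HRQoL after MBSR. Control participants have not received MBSR at any study assessment, since Section 9 offers it to them only once they have completed the study. An analyst following the text could therefore fit the MBSR arm alone.

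The second difficulty does not depend on that reading. Changes from before to after the intervention arise after randomisation and may themselves be affected by arm. Splitting or interacting on them compares participants whom randomisation no longer makes comparable, so they cannot take the moderator role.

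At stake is the trial's stated intention to explain who responds and why. The primary comparison is not at stake.

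**Working it through.** **Inputs from the plan.** Section 5 gives 80 evaluable participants, 40 per group, and 88 enrolled after 10% over-recruitment. The enrolment figure reproduces: 80 × 1.10 = 88. The calculation below uses 40 per arm. The basis of the 80 cannot be checked, because alpha, power, design effect size and SD are not given.

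**Assumptions, not in the plan.** Two-sided alpha 0.05; a constant treatment effect of 0.6 SD; a covariate x correlated ρ with HRQoL change equally in both arms, with ρ from 0 to 0.5; participants treated as independent, although Section 9 describes assignment in groups of 6 to 8.

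**Model.** y = 0.6·arm + ρ·x + √(1 − ρ²)·e, with x and e standard normal. x does not depend on arm, and the arm effect does not depend on x. There is thus no true moderation and no true mediation, and every significant result given either label is a false label. 10,000 trials were simulated per value of ρ.

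| ρ | MBSR-only slope | Arm-by-x interaction | Two-arm joint mediation test |
|---|---|---|---|
| 0 | 0.0499 | 0.0464 | 0.0024 |
| 0.3 | 0.4776 | 0.0475 | 0.0372 |
| 0.4 | 0.7439 | 0.0505 | 0.0482 |
| 0.5 | 0.9236 | 0.0509 | 0.0487 |

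The joint mediation test requires both arm-to-x and x-to-outcome given arm to be significant.

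**Hand check of the one-arm column.** It is simply the power to detect a correlation with n = 40. By Fisher's transformation, power ≈ Φ(atanh(ρ)·√(40 − 3) − 1.96):

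- ρ = 0.3: 0.3095 × 6.083 − 1.96 = −0.077, giving 0.47
- ρ = 0.4: 0.4236 × 6.083 − 1.96 = 0.617, giving 0.73
- ρ = 0.5: 0.5493 × 6.083 − 1.96 = 1.381, giving 0.92

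The same column applies whether x is read as a baseline score (false moderator) or as a symptom change (false mediator). These are one calculation under two labels, not two separate pieces of evidence.

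**What the interaction test can detect.** With x and residual SD both 1, the standard error of a slope difference is √(1/40 + 1/40) = 0.2236, and power = Φ(δ/0.2236 − 1.96):

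- δ = 0.3: 1.342 − 1.96 = −0.618, giving 0.27
- δ = 0.5: 2.236 − 1.96 = 0.276, giving 0.61
- δ = 0.626: 2.80 − 1.96 = 0.84, giving 0.80

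The correct test controls the false label but will detect only large moderation.

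**Timing.** Mediator change to 8 weeks and HRQoL at 8 weeks come from the same visit, so temporal order is not established there even with both arms. HRQoL at 6 and 12 months does follow the 8-week change. Change in UPDRS Part III cannot be formed at 8 weeks or 6 months; at 12 months it shares the visit with HRQoL.

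**The case against.** The strongest reply is that the plan is silent rather than wrong. No passage confines the exploratory analysis to the MBSR arm. Section 5 describes improvement after eight weeks of MBSR in the same sentence as the psychoeducational comparison, and then frames durability of response as MBSR relative to control. Treatment response can therefore mean the between-arm effect. Nor is an unrepeated comparator strong evidence: hypotheses 1b, 2b and 3b omit it too, yet Section 5 shows that they are comparative. All of this stands. A reader might infer that control data will be excluded and that false moderators will be reported; the documents do not support that inference.

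A reader might also infer that the plan ignores the only measure specific to MBSR, because the FFMQ-15 is collected but not named as a mediator. That does not hold either. Section 9.8 also lists an MBSR practice log, and Section 9.11 says engagement and practice will be examined in analyses. Testing the FFMQ-15 as a mediator is a reasonable option, not a correction.

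It is also fair to say that the rates rest on assumed correlations, that the aim is labelled exploratory, and that the sparse analysis text affects every aim.

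Two things survive. The text leaves an analyst free to run a one-arm analysis and call the result moderation or mediation. And giving the moderator role to post-randomisation changes is on the page whichever contrast is meant.

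**Conclusion.** The point holds in a conditional form for the missing contrast and without condition for the moderator role.

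The Exploratory Aim does not specify a control contrast. If it is carried out as an MBSR-only analysis, a purely prognostic factor could be labelled a moderator in about 48% to 92% of trials, against about 5% with an arm-by-baseline interaction. A symptom that co-varies with HRQoL in both arms could be labelled a mediator at the same one-arm rate, against at most about 5% with the two-arm joint test. These figures assume 40 per arm, two-sided 0.05, independent participants and correlations of 0.3 to 0.5. They describe what a literal one-arm analysis would do, not what the plan says will be done.

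Separately, changes in cognition and mood after randomisation cannot be moderators of the randomised effect under either reading.

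Severity is low: the aim is exploratory and Primary Hypothesis 1a is unaffected.

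**What to change.** Replace the analysis wording of the Exploratory Aim with text to this effect:

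- Both randomised arms are used in all moderator and mediator analyses.
- Moderators are baseline scores only, each tested as an arm-by-baseline-score interaction on HRQoL.
- Changes in cognition and mood are tested only as mediators, through the path from arm to mediator and the path from mediator to HRQoL given arm and baseline values. The second path is not protected by randomisation, so the results are interpreted with that caution.
- At 8 weeks the mediator and HRQoL share a visit, so temporal order is not established. UPDRS Part III is available only at baseline and 12 months, so change on that scale is not examined as a mediator at 8 weeks or 6 months.
- Associations found within the MBSR arm alone are called predictors of outcome.

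The moderator item replaces part of the stated hypothesis, and the revision should say so. Adding change in FFMQ-15 as a further mediator is optional.

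The cost is a few sentences; no new data, visits or participants are needed. The downside is that fewer factors will reach nominal significance. With 40 per arm, power is about 0.27 for a standardised slope difference of 0.3, so results should be reported as estimates with intervals rather than as lists of significant factors.
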